8.3 Exploratory Objectives

There are ten exploratory objectives for this study.

- a) The first exploratory objective (EO 1) is to compare proportion of participants with asthma exacerbations by asthma severity group (Mild vs. Moderate-Severe) during the 14 days or 42 days after receipt of LAIV4 or IIV4

Two Mantel-Haenszel Chi-square tests will be used to compare the proportions of asthma exacerbations by treatment and asthma severity groups at 14 and 42 days after receipt of LAIV4 or IIV4, respectively.

- b) The second exploratory objective (EO 2) is to compare the proportion of participants with asthma symptoms and unscheduled albuterol use by asthma severity group (Mild vs. Moderate-Severe) during the 14 days after receipt of LAIV4 or IIV4

Five Mantel-Haenszel Chi-square tests will be used to compare the proportions of each of four asthma symptoms and unscheduled albuterol use by treatment and asthma severity groups.

- c) The third exploratory objective (EO 3) is to compare the proportion of participants that experience a clinically significant decrease in PEFR from baseline during the 14 days after receipt of LAIV4 or IIV4, by asthma severity group (Mild vs. Moderate-Severe).

The Mantel-Haenszel Chi-square test will be used to compare the proportions of a clinically significant decrease ($\geq 20\%$) in PEFR from baseline by treatment and asthma severity groups.

- d) The fourth exploratory objective (EO 4) is describe and compare changes in Peak Expiratory Flow Rate (PEFR) to baseline during the 14 days after receipt of LAIV4 or IIV4, by asthma severity group (Mild vs. Moderate-Severe).

The numerical changes of PEFR from the baseline during the 14 days post vaccination will be graphed and compared by asthma severity group using either t-test or Wilcoxon rank-sum test. Comparisons of mean or median of maximal change from baseline will also be performed between the two treatment groups using either t-test or Wilcoxon rank-sum test and 95% CIs of such differences will be presented.

- e) The fifth exploratory objective (EO 5) is to compare change in Childhood Asthma Control Test (c-ACT) scores (participants aged 5-11 years) or Asthma Control Test (ACT) scores (participants aged 12-17 years) from baseline during the 42 days after LAIV4 or IIV4, by asthma severity group (Mild vs. Moderate-Severe).

The numerical changes of c-ACT and ACT from the baseline during the 14 days post-vaccination will be graphed and compared by asthma severity group using either t-test or Wilcoxon rank-sum test. We may categorize c-ACT and ACT into

well-controlled, poorly controlled, and very poorly controlled groups and run Mantel-Haenszel Chi-square test by treatment and asthma severity groups.

- f) The sixth exploratory objective (EO 6) is to compare asthma symptom days using Preventative Omalizumab or Step-up Therapy for Severe Fall Exacerbations (PROSE) from baseline during the 14 days after vaccination by asthma severity group (Mild vs. Moderate-Severe).

The numerical changes of PROSE from the baseline during the 14 days post-vaccination will be graphed and compared by asthma severity group using either t-test or Wilcoxon rank-sum test.

- g) The seventh exploratory objective (EO 7) is to compare rates of medical utilization for asthma-related symptoms during the 14 and 42 days after LAIV4 or IIV4, by asthma severity group.

Two Mantel-Haenszel Chi-square tests will be used to compare rates of medical utilization for asthma-related symptoms by treatment and asthma severity groups at 14 and 42 days after receipt of LAIV4 or IIV4, respectively.

- h) The eighth exploratory objective (EO 8) is to describe and compare reactogenicity events during the 14 days after receipt of LAIV4 or IIV4, by asthma severity group. Reactogenicity will be assessed by grading on a 0-3 scale, with 0 being used for no events, grade 1 (mild), grade 2 (moderate), and grade 3 (severe).

Reactogenicity is assessed by:

1. Runny nose/nasal congestion
2. Sore throat
3. Chills
4. Earache/ear pain
5. Headache
6. Muscle aches/sore muscles
7. Bone/joint pain
8. Decreased activity/lethargy/fatigue
9. Rash/hives
10. Stomach pain
11. Nausea/vomiting

These events will be graded based on the following scale

1. Grade 0: Symptom did not occur
2. Grade 1: Noticed a change but does not interfere with things done on a normal day
3. Grade 2: Interferes with activity but did not require a doctor's office visit or missed day of school/daycare
4. Grade 3: Prevents daily activity and/or required a doctor's office visit and/or missed day of school/daycare

Fever will be assessed by the following grading scale

1. Grade 0: <100.4 °F
2. Grade 1: 100.4 – 100.9 °F
3. Grade 2: 101 – 102.1 °F
4. Grade 3: >102.1 °F

For each reactogenicity reaction, summary statistics will be performed such as frequencies and percentages for categorical variables and mean/standard deviation or median/interquartile range for continuous variables. Results will be presented as none, mild, moderate and/or severe reactions. There will be statistical comparisons among moderate/severe reactogenicity reactions by treatment groups and asthma severity groups (Mild vs. Moderate-Severe) using Mantel-Haenszel tests.

- i) The ninth exploratory objective (EO 9) is to describe and compare serious adverse events during the 42 days after LAIV4 or IIV4 and assess relatedness to vaccine

For each serious adverse event and assessing relatedness, summary statistics will be performed such as frequencies and percentages for categorical variables and mean/standard deviation or median/interquartile range for continuous variables. The Mantel-Haenszel test will be used for comparisons of proportions of having at least one SAE by treatment groups and asthma severity levels. Listing of the serious adverse events by study LAIV4 or IIV4 groups will also be presented.

- j) The tenth exploratory objective (EO 10) is to describe and compare asthma symptoms and asthma control (PROSE, and c-ACT/ACT scores) among participants with and without a history of allergic rhinitis or hay fever, as a proxy for allergic versus non-allergic asthma.

For each asthma symptom and control, summary statistics will be performed such as frequencies and percentages for categorical variables and mean/standard deviation or median/interquartile range for continuous variables. The Mantel-Haenszel test will be used for comparisons of proportions of having at least one symptom by treatment groups and allergic asthma status (history of allergy rhinitis or hay fever vs. no history of these conditions).

No adjustments will be made to the alpha level (two-sided alpha=0.05) for these exploratory objective analyses.

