2.1.3 Exploratory Objectives

- 1. To compare proportions of participants with asthma exacerbations during the 14 days and 42 days after receipt of LAIV4 or IIV4, by asthma severity group
- 2. To compare the proportions of participants with asthma symptoms and unscheduled albuterol use during the 14 days after receipt of LAIV4 or IIV4, by asthma severity group
- 3. To compare the proportion of participants who experience a clinically significant decrease in PEFR from baseline during the 14 days after receipt of LAIV4 or IIV4, by asthma severity group
- 4. To describe and compare changes in Peak Expiratory Flow Rate (PEFR) from baseline (prevaccination) PEFR after vaccination over time during the 14 days after LAIV4 versus IIV4, by asthma severity group
- 5. To compare change in Childhood Asthma Control Test (c-ACT) score (participants aged 5-11 years) or Asthma Control Test (ACT) score (participants aged 12-17 years) from baseline through 42 days_after LAIV4 or IIV4, by asthma severity group

- 6. To compare asthma symptom days using **Pr**eventative **O**malizumab or **S**tep-up Therapy for Severe Fall Exacerbations (PROSE) from baseline during the 14 days after vaccination by asthma severity group
- 7. To compare rates of medical utilization for asthma-related symptoms during the 14 and 42 days after LAIV4 or IIV4, by asthma severity group
- 8. To describe and compare systemic reactogenicity events during the 14 days after receipt of LAIV4 or IIV4 by asthma severity group
- 9. To describe and compare serious adverse events after LAIV4 vs. IIV4 during the 42 days after vaccination and assess relatedness to vaccine
- 10. To describe and compare asthma symptoms and control among participants with and without a history of allergic rhinitis or hay fever, used as a proxy for allergic versus non-allergic asthma.

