2.3 Exploratory

EO 1: To compare the proportions of participants with asthma exacerbations during the 14 and 42 days after receipt of LAIV4 or IIV4, by asthma severity group (Appendix 1).

EO 2: To compare the proportion of participants with asthma symptoms and unscheduled albuterol use during the 14 days after receipt of LAIV4 or IIV4, by asthma severity group.

EO 3: To compare the proportion of participants who experience a clinically significant decrease in PEFR from baseline during the 14 days after receipt of LAIV4 or IIV4, by asthma severity group.

EO 4: To describe and compare changes in Peak Expiratory Flow Rate (PEFR) from baseline (pre-vaccination) PEFR after vaccination over time during the 14 days after receipt of LAIV4 or IIV4, by asthma severity group.

EO 5: To compare change in Childhood Asthma Control Test (c-ACT) score (participants aged 5-11 years) or Asthma Control Test (ACT) score (participants aged 12-17 years) from baseline through 42 days after LAIV4 or IIV4, by asthma severity group

EO 6: To compare asthma symptom days using Preventative Omalizumab or Step-up Therapy for Severe Fall Exacerbations (PROSE) from baseline during the 14 days after vaccination by asthma severity group.

EO 7: To compare rates of medical utilization for asthma-related symptoms during the 14 and 42 days after LAIV4 or IIV4, by asthma severity group.

EO 8: To describe and compare systemic reactogenicity events during the 14 days after receipt of LAIV4 or IIV4, by asthma severity group.

EO 9: To describe and compare serious adverse events after LAIV4 vs. IIV4 during the 42 days after vaccination and assess relatedness to vaccine.

EO 10: To describe and compare asthma symptoms and control among participants with and without a history of allergic rhinitis or hay fever, used as a proxy for allergic versus non-allergic asthma.

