3.3 Exploratory

EOM 1.1: Proportion of participants with asthma exacerbations by asthma severity group (Mild vs. Moderate-Severe) during the 14 days after receipt of LAIV4 or IIV4

EOM 1.2: Proportion of participants with asthma exacerbations by asthma severity group (Mild vs. Moderate-Severe) during the 42 days after receipt of LAIV4 or IIV4

EOM 2.1: Proportion of participants with asthma symptoms of cough by asthma severity group (Mild vs. Moderate-Severe) during the 14 days after receipt of LAIV4 or IIV4

EOM 2.2: Proportion of participants with asthma symptoms of wheezing by asthma severity group (Mild vs. Moderate-Severe) during the 14 days after receipt of LAIV4 or IIV4

EOM 2.3: Proportion of participants with asthma symptoms of tightness in chest by asthma severity group (Mild vs. Moderate-Severe) during the 14 days after receipt of LAIV4 or IIV4

EOM 2.4: Proportion of participants with asthma symptoms of nighttime awakening by asthma severity group (Mild vs. Moderate-Severe) during the 14 days after receipt of LAIV4 or IIV4

EOM 2.5: Proportion of participants with unscheduled albuterol use to treat asthma symptoms by asthma severity group (Mild vs. Moderate-Severe) during the 14 days after receipt of LAIV4 or IIV4

EOM 3.1: Proportion of participants that experience a clinically significant decrease in Peak Flow measurement during the 14 days after vaccination with LAIV4 or IIV4, by asthma severity group (Mild vs. Moderate-Severe)

Note: A clinically significant decrease in peak flow is defined as a decrease of $\geq 20\%$ in PEFr from baseline PEFr.

EOM 4.1: Numerical changes in Peak Flow when compared to baseline during the 14 days after LAIV4 vs IIV4, by asthma severity group (Mild vs. Moderate-Severe)

EOM 4.2: Description of changes in Peak Flow when compared to baseline during the 14 days after LAIV4 vs IIV4, by asthma severity group (Mild vs. Moderate-Severe)

EOM 5.1 Changes in Childhood Asthma Control Test (cACT) scores (participants aged 5-11 years) or Asthma Control Test (ACT) scores (participants aged 12-17 years) from baseline during the 42 days after LAIV4 or IIV4, by asthma severity group (Mild vs. Moderate-Severe)

EOM 6.1: Maximum number of asthma symptom days using Preventative Omalizumab or Step-up Therapy for Severe Fall Exacerbations (PROSE) from baseline during the 14 days after vaccination with LAIV4 or IIV4, by asthma severity group (Mild vs. Moderate-Severe)

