7.2 Flow Chart

The number of enrolled participants will be presented in a flow chart by site, asthma severity levels, and vaccination group. The number of visits completed and missed will be presented along with the completeness of memory aid. A CONSORT diagram will be presented.

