Proportions of subjects with a clinically significant ($\geq 20\%$) decrease after vaccination in PEFR from baseline (yes or no) will be compared between two treatment groups using a Chi-square test. A postvaccination decrease of ($\geq 20\%$) for each participant will be categorized as Yes if it occurred on one or more days during the 14 days after vaccination. Proportions and difference of proportions by two treatment groups will be reported along with their 95% CIs.

Study staff will document baseline (pre-vaccination) highest of 3 PEFRs on Day 1. Daily highest of 3 PEFR values during Days 1-15 will be documented on the Memory Aid; study staff will enter the highest daily PEFR value into the REDCap database.

SO 3 secondary objective will use the two-side ($\alpha=0.05$) superiority test

No adjustments will be made to the alpha level (two-sided $\alpha=0.05$) for SO2, SO3 secondary objective analyses.

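### EO4 asks how peak flow changes over time by vaccine and severity, but its only explicit vaccine test is an unadjusted comparison of one extreme value per child; a longitudinal model should be added

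*SAP*

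**What the plan says.** SAP 2.3 gives the objective: "To describe and compare changes in Peak Expiratory Flow Rate (PEFR) from baseline (pre-vaccination) PEFR after vaccination over time during the 14 days", by vaccine and by asthma severity group. Protocol 2.1.3 makes the vaccine contrast explicit: "after vaccination over time during the 14 days after LAIV4 versus IIV4, by asthma severity". The matching outcome in SAP 3.3 is "EOM 4.1: Numerical changes in Peak Flow when compared to baseline during the 14 days after LAIV4 vs IIV4", again by severity group. EOM 4.2 is a separate description of the same changes.

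Protocol 8.2 leaves exploratory methods to the SAP, so SAP 8.3(d) is the whole analysis plan for EO4. It has two sentences:

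- The first says that numerical changes over the 14 days "will be graphed and compared by asthma severity group using either t-test or Wilcoxon rank-sum test", so severity is the grouping it names.
- The second turns to the vaccine groups and reads "Comparisons of mean or median of maximal change from baseline will also be performed between the two treatment groups using either t-test", with a rank-sum test as the alternative and 95% confidence intervals for the differences.

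On the data, SAP 8.2 says "Daily highest of 3 PEFR values during Days 1-15 will be documented on the Memory Aid". Staff also record a pre-vaccination baseline, the highest of three efforts, on Day 1. SAP 5.2 rules out site stratification for exploratory objectives, and SAP 8.3 tests them at two-sided 0.05 without multiplicity adjustment. No rule covers missing PEFR days. SAP 7.2 says only that "The number of visits completed and missed will be presented along with the completeness of memory aid".

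**The concern.** The objective has three parts: a vaccine contrast, a time course, and a breakdown by severity. The only sentence that names the vaccine groups reduces each child to a single extreme value, so it can address neither the time course nor severity. The sentence that names severity does not say how up to 15 readings per child enter a two-sample test.

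Three further features follow from using an unadjusted extreme. Its size depends on how many readings the child recorded. Baseline is subtracted but not used as a covariate. Neither the direction nor the unit of the change is defined, although ages run from 5 to 17 and SO3 works in percent.

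PEFR is the only lung-function measure in the schedule of events, and possible wheezing after LAIV is the reason for the trial. A null result from a loosely defined, inefficient test could be read as reassurance.

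**Working it through.** **1. Objective against method.**

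| Part of EO4 | First sentence of 8.3(d) | Second sentence of 8.3(d) |
|---|---|---|
| Vaccine contrast | Not named; severity is the stated grouping | Yes |
| Severity | Yes | No |
| Change over time | Graphed; the test names no day, per-child summary or repeated-day method | No: one value per child |
| Baseline | Subtracted | Subtracted, no covariate |

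**2. The plan's own figure.** No power is given for EO4. The only power figure is 81.1% for the primary test (SAP 4.2). With 12% in each arm, 135 per arm, margin 10% and one-sided 5%: SE = √(2 × 0.12 × 0.88 / 135) = 0.0396; 0.10/0.0396 − 1.645 = 0.88; power = Φ(0.88) = 81.1%. It reproduces. It says nothing about EO4 beyond fixing 135 per arm.

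**3. The extreme grows with the number of readings.** If daily values have total SD 1 and within-child correlation ρ, the expected maximal fall with no vaccine effect is √(1 − ρ) × E(k), where E(k) is the expected maximum of k standard normals. E(14) = 1.70, E(10) = 1.54, E(7) = 1.35. At ρ = 0.5: 0.707 × 1.70 = 1.20 for 14 readings and 0.707 × 1.54 = 1.09 for 10. With a day-to-day SD of 10%, 14 readings rather than 10 add about 10% × (1.70 − 1.54) = 1.6% of PEFR to the expected fall.

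**4. When that matters.** Simulation set-up, all assumed except the sample size: 135 per arm, up to 14 readings, baseline 150-450 L/min, and an SD of 10% each for baseline error, child-level drift and day-to-day noise. With no vaccine effect:

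- Equal completeness: the maximal-change test rejects about 5%, as it should.
- 14 v 12 readings by arm: about 7%.
- 14 v 10: about 11%.
- Mean-based analyses stay near 5% throughout.

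In another assumed structure, where baseline and all diary days are equally correlated (ρ from 0.5 to 0.9), the two unequal cases give 8-9% and 20-21%.

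**5. Power depends on the shape of the effect.** Same set-up as step 4, complete diaries:

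| Effect of LAIV4 | Maximal absolute change | Maximal fall on log or percent scale, baseline-adjusted | Mean log PEFR, baseline-adjusted |
|---|---|---|---|
| 5% fall on every day | 61% | 81% | 86% |
| 15% fall on 2 days | 81% | 95% | 26% |

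Repeat simulations of these assumptions gave 54% to 63% for maximal absolute change and 83% to 86% for the mean in the first row. The spread in the former exceeds simulation error (√(0.6 × 0.4 / 1500) = 1.3 points), so details the assumptions leave open matter and the figures are approximate. One repeat gave 68% v 25% (maximal absolute change v mean) for the second row. It also gave 99% v 44% for a 20% fall on 2 days, 52% v 39% for a 10% fall on 4 days, and 69% v 24% when one LAIV4 child in five falls 40% for 3 days.

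**The case against.** The best defence is that maximal change is a sensible safety summary. SO3 also counts a fall on one or more days, and step 5 shows that the extreme beats the 14-day mean when the fall is brief or confined to a few children. This stands. A reader might infer that maximal change should be dropped or reduced to description; that would give up power for the reactions it detects best.

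Other points also have weight:

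- EOM 4.1 allows the first sentence to mean vaccine contrasts within severity groups. That is possible, but the test would still lack a day, a summary or a method for repeated days.
- A reader might infer that child-days would be pooled as independent, or tested one day at a time, with inflated error. The SAP specifies neither. It is silent, and that silence is the defect.
- Unequal completeness is not shown. Both arms get the same Day 4, 8 and 15 contacts (Protocol 4.8) and a meter with time-stamped memory (Protocol 4.6). The bias is therefore conditional, though possible in an open-label diary study.
- Absolute units are an inference from the word numerical. Percent maximal change raised power for the constant 5% fall from 54% to 69% in one simulation and from 63% to 80% in another, so much of the loss is a matter of scale.
- Under the step 4 assumptions baseline adjustment adds little to the mean (83% to 86%). It adds more where baseline and diary days are equally correlated: 78% to 97% at ρ = 0.5 (0.25 SD shift), 85% to 88% at ρ = 0.9 (0.12 SD shift).
- The daily changes will be graphed and described. That meets the descriptive half of the objective but not the comparative half.

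**Conclusion.** The point holds as a mismatch between an exploratory objective and its analysis. The only explicit vaccine test in SAP 8.3(d) cannot answer a question about change over time by severity, and the other sentence leaves its contrast and its handling of repeated days undefined.

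The consequence depends on the effect. For a small, sustained fall the planned test is clearly weaker than a baseline-adjusted analysis of all days (about 60% v 85% for a constant 5% fall). For a brief or minority fall it is stronger than the all-days mean, though still weaker than the same extreme on a log or percent scale with baseline adjustment. False positives exceed 5% only if completeness differs by arm: about 7% to 11% in the cases tried, and up to 21% in the alternative structure. All of this rests on assumed PEFR variances, correlations and completeness, for which the documents give no values.

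A reader might infer a threat to the trial's main findings. The documents do not support that: EO4 is exploratory, and neither the primary nor any secondary conclusion depends on it.

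**What to change.** Amend SAP 8.3(d), before PEFR is compared by arm, as follows:

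- Add a repeated-measures mixed model on log PEFR. Include vaccine, day, vaccine × day, log baseline PEFR, severity, vaccine × severity, age group and site, and state in advance how repeated days within a child are handled. Report the LAIV4/IIV4 percent difference with 95% CI by day and averaged over Days 2-15, overall and by severity.
- Keep the maximal-change comparison as a companion test. Define it as the largest fall on the log or percent scale, adjusted for baseline. Report the number of readings by arm beside it, because a change of scale does not remove its dependence on that number.
- Say which contrast the first sentence of 8.3(d) intends, and note in SAP 5.2 that this model includes site.

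No new data are needed. The cost is SAP wording and one more model to specify, fit and report.

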4.3.6 Visit 6 (Day 43 + 7) – Contact [phone call(s), email(s), and/or text message(s)]

- Concomitant medications review
- Unsolicited symptoms review
- Medical services utilization review
- Obtain serious adverse event (SAE) information
- Post-vaccination asthma clinical symptoms review and symptom scores
 - Asthma control assessment (c-ACT/ACT, as appropriate by age)

Table 1: Schedule of Events

Study Visit	Enrollment Visit 1 (Vaccination)	Visit 2	Visit 3	Visit 4	Visit 5	Visit 6
Study Day	1	4	8	15	29	43
Visit Window (Days)	n/a	3-6	7-11	15-20	26-32	43-50
Type of Visit	In –person Clinic	Reminder only	Contact	Contact	Contact	Contact
Obtain Informed Consent through parental permission	X					
Obtain Assent (if applicable per site's IRB requirement)	Х					
Review Eligibility Criteria	Х					
Document Prior Year Flu Vaccination and present year influenza vaccine status for children 5-8 years	Х					
Review Medical History	Х					
May perform targeted physical exam	X					
Review Asthma History	X					
Assess asthma clinical symptoms ^a (PROSE)	X			X		
Assess asthma control ^b (c- ACT/ACT)	X					Х
Asthma severity classification ^c	Х					
Concomitant Medications ^d	Х		Х	Х	Х	Х
Urine or serum pregnancy test ^e	Х					
Oral temperature	Х					
Sex, Height, Weight, BMI	Х					
Peak Flow Measurement ^f	Х		Х	X		
Enrollment and Randomization ^g	Х					
Study Vaccination	Х					
Post vaccination evaluation period (at least 20 minutes)	X					
Distribute Memory Aid and other Materials	X					
Memory Aid Review (solicited symptoms)			Х	X		
SAE, unsolicited symptoms, and Medical Services Utilization ^h	X		Х	Х	Х	Х

^a Asthma clinical symptoms assessed using the PROSE questionnaire.

^b Asthma control assessed using the c-ACT or the ACT, as appropriate by age.

^c See section 4.4 in the protocol, for categories of asthma severity.

^d All current medications taken within 28 days prior to signing the informed consent form and through Day 43 (Visit 6).

^e Will be performed on all post-menarchal females within 24 hours before vaccination.

^fThe highest of 3 peak flow measurements will be recorded.

^g Participants will be randomized 1:1 to LAIV4 or IIV4; stratified by asthma severity and age stratum ^hMedical services utilization to include visits to doctor, urgent care, emergency room, hospitalization.

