4.6 Individual Peak Expiratory Flow Rate (PEFR) Evaluations

Participants will be trained on the "at home" performance of PEFR using a digital hand held device purchased by study funds and that participants will get to keep after completing the study. The device is easily learned, and it can provide an objective measure of control of asthma symptoms. Typically, a participant's PEFR is measured while standing by the highest of 3 efforts. These measurements should be completed in the evening, before taking daily controller medication, to minimize variations that may be influenced by diurnal changes. Additionally, the PEFR maneuver should be attempted after completion of the two surveys that assess asthma control (c-ACT/ACT and PROSE) to avoid bias in the recording of daily symptoms. All efforts will be made to minimize variation in technique; training in proper digital peak flow meter use will be accomplished at study enrollment and reviewed at each study call.

For this study, all sites will provide participants with a digital peak flow meter. This device has an automatic memory for peak flow measurements and each entry is marked with a time stamp; thus, participants will be instructed to record their daily PEFR data measurements on their memory aid until day 15.^{25,26}

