4.8 Monitoring Vaccine Safety in the First 15 Days

On the vaccination day and for the next 14 days post-vaccination (until day 15), all participants will be monitored daily by their parent(s) or legal guardian(s) and the information will be recorded using memory aids provided at the enrollment visit. Daily reactogenicity, including measurement of nighttime awakening, and unscheduled albuterol use and two validated questionnaires will be completed (c-ACT/ACT and PROSE). PROSE will be assessed at baseline (Day 1) and on Day 15.

In addition to the two questionnaires above, several predefined events that could occur after vaccine administration will also be recorded for 14 days after vaccination (through day 15). These will include fever (oral temperature $\geq 100.4^{\circ}$ F), asthma symptoms, and other respiratory and systemic symptoms. Medication receipt, new prescriptions for asthma medications, and any previously unscheduled healthcare utilization (medical office visits, ED visits, hospitalizations) will also be documented on the reaction form. To ensure compliance with the reaction assessment, parents will be called, emailed through REDCap, or receive text messages on Days 4, 8 and 15 by the study staff.

On the day of vaccination and during the first 14 days (until day 15) after vaccination, if the participant reports an increase in their symptoms and an increase in the need for medications for their asthma, the family will be instructed to contact the study staff, so medical records can later be collected, if needed. If at any point a study participant is experiencing symptoms of any asthma exacerbation, the participant or their parent will be instructed to contact their primary care provider (PCP) and inform study staff of this encounter.

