4.9 Extended follow-up for days 16-43

After the initial 15-day follow up after vaccination, there will be an extended surveillance period for safety assessment from day 16 after vaccination for a total of 42 days (Day 43). This will be accomplished by a telephone call, text messaging, or email through the REDCap system to the parents of the participants, depending on their preference and their availability, at day 29 and at day 44 to determine the status of asthma control. On Day 29, participants will be queried about concomitant medications, unsolicited symptoms, serious adverse events, and medical services utilization. On day 44, participants will be queried about concomitant medications, unsolicited symptoms, serious adverse events, and medical services utilization. On day 44, participants will be queried about concomitant medications, unsolicited symptoms, serious adverse events, and medical services utilization. On day 44, participants will be queried about concomitant medications, unsolicited symptoms, serious adverse events, and medical services utilization. On day 44, participants will be queried about concomitant medications, unsolicited symptoms, serious adverse events, and medical services utilization.

During the extended follow up period, parents/legal guardian will be instructed to contact the study staff if the participant has an unscheduled medical visit for management of asthma symptoms or a new asthma medication prescribed.

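### SAP 8.3 (exploratory only): EO 5 uses a 14-day window for scores scheduled only at Visits 1 and 6; EO 5 and EO 6 do not clearly name the vaccine contrast; EO 1–3, EO 7 and EO 8 plan no within-severity vaccine difference or interval

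*SAP*

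**What the plan says.** EO 5 concerns change in the asthma control score: c-ACT at ages 5–11, ACT at ages 12–17. The SAP gives its window four times:

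- SAP 2.3, objective: "from baseline through 42 days after LAIV4 or IIV4, by asthma severity group".
- SAP 3.3, EOM 5.1: "scores (participants aged 12-17 years) from baseline during the 42 days after LAIV4 or IIV4".
- SAP 8.3, lead-in to EO 5: "from baseline during the 42 days after LAIV4 or IIV4, by asthma severity group (Mild vs. Moderate-Severe".
- SAP 8.3, analysis sentence: "The numerical changes of c-ACT and ACT from the baseline during the 14 days post-vaccination will be graphed and compared by asthma severity group", by t-test or Wilcoxon rank-sum test.

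Protocol 4.3.1 places c-ACT/ACT at Visit 1. Protocol 4.3.6 lists it at Visit 6: "Asthma control assessment (c-ACT/ACT, as appropriate by age". Table 1 marks only those two visits. Visit 4 (Day 15, Protocol 4.3.4) lists PROSE but not c-ACT/ACT.

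The other exploratory analyses in SAP 8.3:

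- **EO 4 (PEFR):** a sentence of the same form, followed by a separate comparison of the two treatment groups with 95% CIs.
- **EO 5:** followed only by an optional Mantel-Haenszel test on categorised scores, by treatment and severity.
- **EO 6 (PROSE):** a sentence of the same form, with nothing added.
- **EO 1, 2, 3 and 7:** two, five, one and two Mantel-Haenszel tests by treatment and severity.
- **EO 8:** Mantel-Haenszel tests without a count, plus frequencies and percentages.

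For comparison, SO 2 and SO 3 (SAP 8.2) plan differences of proportions with 95% CIs.

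**The concern.** There are three gaps, in descending order of certainty.

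(a) The EO 5 analysis sentence asks for a quantity that the visit schedule does not produce.

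(b) The two-sample tests for EO 5 and EO 6 name one two-level grouping, severity. Taken literally, they show whether mild and moderate-severe children change differently. EOM 5.1 and EOM 6.1 refer to LAIV4 or IIV4. Two programmers could produce different tables from the same sentence.

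(c) Objectives worded by severity, in a trial whose SAP title refers to varying levels of severity and which randomises within severity strata, would be tested with a vaccine result pooled over severity. The difference between vaccines in moderate-severe children, and its precision, would not be a planned output.

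**Working it through.** **(a) Window.** Three SAP statements say 42 days and one says 14. A change score needs two measurements, and the scheduled ones are Day 1 and Visit 6 (Days 43–50). No scheduled pair spans 14 days. The ACT items in Protocol Appendix 13.2 ask about the past 4 weeks, so a Day 43 ACT looks back to about Day 43 − 28 = Day 15. It cannot stand in for a score covering the first 14 days.

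**(b) Contrast.** EO 4, EO 5 and EO 6 share one sentence form. In EO 4 the treatment comparison is introduced as an addition to that sentence, which suggests that the sentence itself was not meant to supply it. EO 5 adds only an optional test, and EO 6 adds none.

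**(c) Number of tests.** EO 1 has 2 time points, EO 2 has 5 outcomes, EO 3 has 1 outcome and EO 7 has 2 time points: 2 + 5 + 1 + 2 = 10. The SAP states 10 tests. One test per outcome or time point implies one severity-pooled vaccine result each, not one per stratum.

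**The plan's own figure.** The inputs from SAP 4.2 are 12% in both arms, 135 per arm, margin 10 points and one-sided alpha 0.05. Then SE = √(2 × 0.12 × 0.88 / 135) = 0.0396, and power = Φ(0.10/0.0396 − 1.645) = 81.1%, as stated. This confirms the inputs. The present point does not change that figure.

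**Precision of the missing estimates.** The documents give no severity split, so it is assumed. At 12% in both arms, the 95% half-width is 1.96 × √(2 × 0.12 × 0.88 / n):

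| Children per arm | Half-width (points) |
|---|---|
| 40 moderate-severe | 14.2 |
| 68 moderate-severe | 10.9 |
| 95 moderate-severe | 9.2 |
| 135 (pooled) | 7.8 |

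**Illustration with unequal strata (all risks assumed).** Mild 8% in both arms, 67 per arm; moderate-severe 28% LAIV4 and 16% IIV4, 68 per arm.

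- IIV4 overall: (67 × 8 + 68 × 16)/135 = 12.0%. LAIV4 overall: (67 × 8 + 68 × 28)/135 = 18.1%.
- Pooled difference: 12 × 68/135 = +6.0 points, half-width 8.3.
- Mild: 0, half-width 1.96 × √(2 × 0.08 × 0.92/67) = 9.2.
- Moderate-severe: +12, half-width 1.96 × √((0.28 × 0.72 + 0.16 × 0.84)/68) = 13.8. It runs from 18.0 with 40 per arm to 11.7 with 95.
- Simulated power (200,000 trials, two-sided 0.05): Mantel-Haenszel 29%, chi-square within moderate-severe 40%.

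Neither test is well powered, so the gain is in estimation, not detection.

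**Cell sizes if c-ACT and ACT are separated.** ACT users come only from 2019–20, because the first season took ages 5–11 (SAP 4.1). If 20% to 50% of 135 per arm use ACT and severity splits evenly (assumed), an ACT-by-severity cell has about 14 to 34 children per arm. The half-width 1.96 × √(2/n) is then 0.75 to 0.48 SD, or about 0.79 SD at the small end with a t quantile.

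**Number of intervals added.** EO 8 has 11 symptoms plus fever, 12 outcomes. The total is 2 + 5 + 1 + 2 + 12 = 22 outcomes, so 44 stratum intervals. EO 4–6 add at least 2 + 4 + 2 = 8 (two instruments in EO 5). That makes 52, and 52 × 0.05 = 2.6 would be expected to exclude zero if there were no differences.

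**The case against.** **The window is one wrong number.** It was probably carried over from the EO 4 and EO 6 sentences, where 14 days is right, and the SAP's other three statements show the intent. That lowers the stakes, but the analysis sentence is still wrong as it stands.

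**The severity phrase can be read otherwise.** In most of the SAP 2.3 objectives similar wording follows a mention of both vaccines, so SAP 8.3 may intend a vaccine comparison within severity. For EO 6 the objective itself names no vaccine, so the literal test agrees with it, though not with EOM 6.1. This stands: (b) is an unstated contrast, not a proven wrong one. Nor does any section plan to pool c-ACT and ACT; EOM 5.1 assigns them by age.

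**Percentages will probably be tabulated.** A reader might infer that moderate-severe children would get no vaccine estimate at all. The documents do not support that. EOM 1.1–3.1 and 7.1–8.1 (SAP 3.3) are proportions or rates by severity, and the opening of SAP 8 promises frequencies and percentages, repeated for EO 8. Arm-by-severity percentages are the natural output, and the difference is then a subtraction. What is missing is the stated difference and its interval. Leaving these out of an exploratory analysis contradicts nothing.

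**The protocol does not contradict Table 1.** A reader might infer that it does from three places:

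- Protocol 4.6: "the PEFR maneuver should be attempted after completion of the two surveys that assess asthma control (c-ACT/ACT and PROSE". This sets an order, not a day, and fits Visit 1.
- Protocol 4.8: "two validated questionnaires will be completed (c-ACT/ACT and PROSE". It gives no day for c-ACT/ACT and dates only PROSE.
- Protocol 4.9: "at day 29 and at day 44 to determine the status of asthma control". It does not name the instrument, and Day 44 lies inside the Visit 6 window.

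These are unspecific, or a one-day nominal difference.

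**The masking illustration is chosen.** It puts LAIV4 at about 18% overall against the plan's 12%. It shows what a pooled result can conceal, not what is expected.

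**Conclusion.** The point holds, for exploratory objectives only. It does not affect the primary or secondary analyses, the margin or the sample size, and should not be read as doing so.

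Part (a) is a definite error: a 14-day analysis of scores scheduled at Day 1 and Days 43–50. Part (b) is an ambiguity whose literal reading gives a severity contrast. The EO 4 pattern favours that reading without settling it. Part (c) is an omission: one severity-pooled test per outcome or time point for EO 1–3 and EO 7, the same type of test for EO 8, and no planned within-severity difference or interval.

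The size of (c) rests on assumptions. With 40 to 95 of 135 per arm moderate-severe, the half-width is about 9 to 14 points at 12% in both arms, and about 12 to 18 points under the higher risks in the illustration. The correction is worth making because it costs little and severity is already a randomisation stratum.

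**What to change.** In SAP 8.3:

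- **EO 5:** replace the 14-day window by Day 1 to Visit 6 (Day 43, window 43–50), and state that c-ACT and ACT are analysed separately.
- **EO 4–6:** state that the contrast is LAIV4 versus IIV4 within each severity group (mild; moderate-severe), reported as a mean or median difference with a 95% CI.
- **EO 1–3, EO 7, EO 8:** also report LAIV4 minus IIV4 risk differences with 95% CIs separately for mild and moderate-severe, keeping Mantel-Haenszel as the pooled summary. Score-type intervals suit sparse cells, mainly in EO 8.

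Optional tidying: give the c-ACT/ACT day in Protocol 4.8 and align Day 44 in Protocol 4.9 with Table 1.

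The cost is SAP wording and extra table rows from data already collected. The intervals will be wide, ACT cells small, and about 2 to 3 of roughly 52 unadjusted intervals would exclude zero by chance. Neither an isolated exclusion nor a wide interval covering zero should be over-read.
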